### Measures

Clinician characteristics gathered from the health system included: sex, degree (MD, DO, NP), specialty and years since last clinical training. Patient characteristics including sex, race, ethnicity, insurance type and smoking status, were drawn from the EHR.

TMCP-specific variables include training participation, online learning module completion and quiz score. Use of the TMCP flowsheet by clinicians during visits was measured for 6-months after training to indicate use of the TMCP. Clinician's documentation of any portion of the TMCP flowsheet was counted as 'use'.

Outcome measures include contact by the QL or FFS among those patients that accepted a referral and provision of brief advice. Secondary outcomes include medication orders (i.e. varenicline, bupropion or nicotine replacement therapy) enrollment among those referred to cessation support (QL or FFS), and quit attempts. For this study, a quit attempt is defined as a change in smoking status from current smoker to former smoker and documentation of a quit date in the EHR. Quit attempts are evaluated for all smokers.

We report the rates of Ask, Advise, Assessment of readiness to quit and acceptance of a referral (Connect) to tobacco cessation assistance for the AAC intervention (AAC only) period and the time period after the TMCP intervention (AAC+TMCP). Each of these indicators is measured from discrete fields in the EHR. As shown in Figure 1, the timing of the AAC and the TMCP intervention implementation and the time periods between the two interventions varied.

We assessed patients' experiences with the clinic's processes. The survey samples included at least 17 smokers from each of the eight sites for the AAC only and the AAC+TMCP study periods. Patients who attended a primary care visit during a specified period were invited to complete the survey by web or phone, depending on the participant's preferred contact method. The survey included 11 items about being treated with respect, feeling listened to, and whether the advice was helpful. Responses were measured using a 5- point Likert scale rating from excellent to poor.

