1 Using a teachable moment communication process to improve outcomes of quitline referrals  
2  
3 Principal Investigator: [name], PhD,  
4 Department of Family Medicine  
5 Oregon Health & Science University  
6 [name]  
7 [name]  
8 [contact]  
9  
10 Site Principal Investigator: [name], MD, MS, MetroHealth Health System  
11 [name]  
12 [name]  
13  
14 Co-Investigators:  
15 [name], PhD, MetroHealth  
16 [name], MD, MetroHealth  
17 [name], PhD, MPH, Case Western Reserve University  
18 Study Staff:  
19 [name], MS, MBA, MetroHealth  
20 [name], MPA, Case Western Reserve University  
21 [name], MPH, Case Western Reserve University  
22  
23 Institution receiving the PCORI award: Oregon Health & Science University, Portland Oregon, USA  
24  
25 PCORI award number: IHS-1503-29879-IC  
26 ClinicalTrials.gov registration: NCT02764385  
Last updated December 11, 2020  
27

28 **Project summary**

29 **Background:** Guidelines urge primary care practices to provide routine tobacco cessation care.  
30 Implementation of effective and sustainable strategies is lacking, especially for socially and economically  
31 disadvantaged populations. We test a systems-based approach that engages the medical assistant that  
32 assesses the patient's vital signs at the beginning of a routine visit and the added effect of a clinician-  
33 based approach that draws on a relationship-centered communication strategy.

34 **Objectives:** This project aimed to: 1) Improve delivery and documentation of smoking cessation care to  
35 disadvantaged patients using an Ask-Advise-Connect (AAC) systems-based approach, 2) Test the effect  
36 of combining the clinician-based Teachable Moments Communication Process (TMCP) intervention with  
37 AAC on advice to quit, referrals to cessation counseling and provision of tobacco cessation medications  
38 and 3) Examine the narratives of patient subgroups to understand and improve the referral experience.

39 **Methods:** This study engaged a healthcare system and eight primary care clinical sites with two  
40 interventions. The 3-month period before the AAC intervention represented a pre-AAC control period  
41 (baseline). All sites received the AAC strategy throughout the study and its use was evaluated for a  

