42 minimum of 6 months (AAC-only). Next, using a group-randomized stepped-wedge design, sites received  
43 the TMCP intervention (AAC+TMCP). The patient population is 40% Medicaid, 23.9% Medicare, 6.1%  
44 uninsured and 30% commercially insured. The AAC strategy involved changes to the electronic health  
45 record (EHR), a new role for medical assistants and a new capacity to send electronic referrals to the  
46 Quitline (QL) to enroll patients in tobacco cessation counseling. Next, in accord with their practice's  
47 place in the stepped wedge design, 44 of the 60 eligible clinicians attended training in the TMCP, an  
48 approach to counseling patients to quit tobacco aligned with patient readiness. Generalized linear  
49 models tested the effect of interventions on immediate outcome measures of process, including  
50 delivery of advice, offer of assistance and referrals accepted, and QL contact and enrollment rates.  
51 Receipt of tobacco cessation medications and quit attempts were also assessed. The primary outcome  
52 was QL contact. In-depth interviews were conducted with 55 patients referred to the QL to explore their  
53 experiences and identify opportunities to improve the referral process.

54

55

56

57

58

59

60  
61  
62  
63  
64  
65  
66  
67  
68  
69  
70  
71  
72  
73  
74  
75  
76  
77  
78  
79  
80  
81  
82  
83  
84  
85  
86

87 **Rationale & background information**

88 Smoking is the leading cause of preventable mortality. Smoking rates in the United States have  
89 declined, but remain particularly high among socially and economically disadvantaged populations, who  
90 are also less likely to use supports for quitting smoking. Therefore, implementing and evaluating  
91 strategies that work for socially and economically disadvantaged populations is a high priority. Among  
92 U.S. smokers, 59% report seeing a primary care clinician at least yearly, making primary care a major  
93 avenue for providing tobacco cessation assistance tailored to each patient's medical history. However,  
94 evidence-based interventions addressing tobacco cessation are generally underused. New healthcare  
95 policy initiatives, requiring assessments of tobacco use and assistance to quit, call for integration of  
96 tobacco cessation interventions into primary care.

97 Referral to quitlines (QLs) that provide evidence-based, effective and cost-efficient assistance with  

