98 smoking cessation, is recommended as an effective strategy for tobacco cessation assistance.  
99 However, a clinician's recommendation to call a QL typically results in poor calling rates (range 1.6% -  
100 19%). Yet, success rates increase when QLs proactively call patients after receiving a direct clinician  
101 referral (by fax or electronically). Still, clinicians underutilize direct referrals, potentially due to low  
102 integration of the referral system into the office workflow. Research demonstrates the feasibility of  
103 closed loop electronic referrals using the electronic health record (EHR) for connecting with QLs. The  
104 advantage of eReferral is that patient information is securely transmitted between the referring clinician  
105 and the QL, and QL enrollment and counseling completion records become part of the patient medical  
106 record.

107 Two intervention approaches for providing patients with assistance for smoking cessation have  
108 shown promise in the primary care setting. Ask-Advise-Connect (AAC) is a systems-based approach that  
109 uses the EHR to remind clinicians to ask about tobacco use and give advice to quit, and then  
110 electronically connects interested smokers to tobacco cessation counseling services such as the QL. The  
111 Teachable Moment Communication Process (TMCP) is a relationship and communication-focused  
112 strategy designed to counsel patients about behavior change by responding in a way both appropriate  
113 to and aligned with patient's readiness for a change. These approaches are feasible, complementary  
114 and have the potential to be integrated into a health system to improve sustainability.

[figure not shown]
115 Ask-Advise-Connect (AAC): This proactive, direct messaging EHR-to-QL referral approach has been  
116 shown to increase the number of tobacco users receiving QL treatment by 13- to 30-fold. However, a  
117 major drawback of AAC is a low rate of contacting referred patients. Prior studies found that the QL was  
118 able to contact less than 42% of referred patients. This poor contact rate diminishes the sustainability of  
119 the approach, and is likely due to referring patients inappropriately, ignoring cessation readiness.

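### The Project summary and Measures define the primary outcome differently, and contact among accepted referrals measures referral yield, not smokers reached

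*Combined protocol and SAP*

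**What the plan says.** **Project summary, Methods.** The primary outcome "was QL contact. In-depth interviews were conducted with 55 patients" (the quotation runs on into the next sentence). This is a single outcome, QL only, with no denominator. The same paragraph lists the modelled process measures as "delivery of advice, offer of assistance and referrals accepted, and QL contact and enrollment rates".

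**Project summary, Objectives.** The second objective is the effect of combining TMCP with "AAC on advice to quit, referrals to cessation counseling and provision of tobacco cessation medications". Referral is thus itself something the trial tests.

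**Research methods, Measures.** The outcome measures include "contact by the QL or FFS among those patients that accepted a referral and provision of brief advice". A separate sentence then lists the secondary outcomes: medication orders, enrollment among those referred, and quit attempts. The word primary does not appear. Quit attempts are assessed in all smokers, and the rate of referral acceptance (Connect) is reported for both periods.

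**Participating sites and randomization.** The EHR chooses the destination from payer data. Adults on Medicaid or without insurance, and pregnant patients, qualify for the free QL; the others go to FFS.

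**Statistical analyses and Study sample.** The model is for the log odds of an unnamed outcome in a patient, by intervention status, and the first of three analyses is by intention to treat. The sample is described in visits.

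**The concern.** There are two problems. First, a reader cannot tell which result is the primary one. QL contact and QL-or-FFS contact are different outcomes in different patients, the rank of brief advice is unclear, and the unit could be the patient or the visit.

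Second, contact is counted only in patients who accepted a referral. Acceptance comes after the intervention, and TMCP is meant to act on it: the Rationale expects TMCP to move patients toward readiness and to raise the share of appropriate referrals, and the flowsheet section lets clinicians order QL or FFS themselves. If TMCP changes who accepts, the contact odds ratio compares two possibly different mixes of patients. The intention-to-treat label does not alter this, because the outcome is conditioned on a later event.

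The risk is that the contact odds ratio is read as the answer to whether adding TMCP reached more smokers. Alone, it cannot answer that.

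**Working it through.** The available text gives no sample size, power or event count, so there is no figure of the plan's own to reproduce.

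**1. Do the two definitions cover different patients?** Payer mix (Project summary): Medicaid 40%, Medicare 23.9%, uninsured 6.1%, commercial 30%.
- QL-eligible by payer: 40 + 6.1 = 46.1%.
- Not eligible, so FFS: 23.9 + 30 = 53.9%.

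This is the whole patient population. Pregnancy and dual cover are ignored, and the mix among smokers is not given.

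**2. Can the effect among acceptors differ from the effect per smoker?** Let a be acceptance and c contact among acceptors, with 0 for AAC only and 1 for AAC+TMCP. Contact per smoker is p = a × c. The odds ratio (OR) among acceptors is [c1/(1 − c1)] / [c0/(1 − c0)], and the OR per smoker has the same form in p. Acceptance rates are not in the documents, so all values of a are assumed. The base c0 = 42% is the upper bound that the Rationale quotes from prior AAC studies, where the quitline was "able to contact less than 42% of referred patients".

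| Assumed change | a (%) | c (%) | OR among acceptors | Contacts per 1000 smokers | OR per smoker |
|---|---|---|---|---|---|
| Acceptance unchanged | 20 → 20 | 42 → 52 | 1.50 | 84 → 104 | 1.27 |
| Small rise, added acceptors contacted at 64% | 20 → 22 | 42 → 44.0 | 1.09 | 84 → 96.8 | 1.17 |
| Small rise, added acceptors contacted at 20% | 20 → 22 | 42 → 40.0 | 0.92 | 84 → 88 | 1.05 |
| Large rise, added acceptors contacted at 24% | 20 → 30 | 42 → 36 | 0.78 | 84 → 108 | 1.32 |
| Fall in acceptance | 20 → 10 | 42 → 52 | 1.50 | 84 → 52 | 0.60 |

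Fourth row in full:
- p0 = 0.20 × 0.42 = 0.084; p1 = 0.30 × 0.36 = 0.108.
- Added acceptors: (0.108 − 0.084)/0.10 = 24% contacted.
- OR among acceptors: (0.36/0.64)/(0.42/0.58) = 0.78.
- OR per smoker: (0.108/0.892)/(0.084/0.916) = 1.32.

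With baseline acceptance of 10% to 30% and the same relative rise, the OR among acceptors stays at 0.78 and the OR per smoker runs from 1.30 to 1.34.

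**3. Break-even.** Contacts per smoker are unchanged when a1/a0 = c0/c1. For a 6-point fall in contact:
- base 30%: 0.30/0.24 = 1.25, a 25.0% relative rise in acceptance;
- base 42%: 0.42/0.36 = 1.167, a 16.7% rise;
- base 60%: 0.60/0.54 = 1.111, an 11.1% rise.

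In the other direction, a rise in contact from 42% to 52% is cancelled if acceptance falls to 0.42/0.52 = 0.81 of its former level.

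**4. Observation windows.** Study Design and Timing says that time in each condition varied by clinic. For an outcome of any contact in the period, unequal windows alone create an effect. With an assumed constant 8.4% per 6 months and no TMCP effect, 12 months gives 1 − 0.916² = 16.1%. Against a 6-month period, the spurious OR is (0.161/0.839)/(0.084/0.916) = 2.09.

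The first AAC training was on 15 February 2017. Seven further steps of about 2 weeks (98 days) put the last near 24 May 2017. That is 154 days, about 5 months, before the first TMCP training on 25 October 2017.

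**The case against.** Contact among referred patients is a deliberate target: the Rationale names low contact of referred patients as the drawback of AAC, and the denominator missing from the summary can be inferred from there. Measures ranks contact and brief advice by placing them ahead of the secondary outcomes. The plan already has a smoker-level outcome, quit attempts, and models accepted referrals separately. Counting every unreferred smoker as a failure makes per-smoker contact largely a referral outcome.

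The illustration is also constructed. The 42% comes from studies that the Rationale criticises for ignoring readiness, which this trial assesses before referring. The reversals need added acceptors who are harder to reach, or fewer acceptors. The Rationale expects readier patients and likelier contact, and when added acceptors do better the two odds ratios agree (1.09 and 1.17). In addition, the medical assistant, who takes "vital signs at the beginning of a routine visit", may make the referral before that visit's TMCP, so acceptance may move little.

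Most of this stands, and it limits the point. It does not remove it. An implied pair of leading outcomes still conflicts with a single named primary, and QL still differs from QL or FFS. Odds ratios for acceptance and for contact, read side by side, give no confidence interval for smokers reached. Quit attempts are a different outcome from contact.

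A reader might infer that contact among acceptors is an invalid outcome, or that the trial's contact result points the wrong way. The documents support neither: the measure is sound as referral yield, and no trial rates are given.

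**Conclusion.** The point holds as a should-fix. The mismatch between the Project summary and Measures is certain from the text. It matters because roughly half the patient population (53.9% by payer, with the limits noted) falls outside QL eligibility. It is equally clear that contact and enrollment among acceptors are conditioned on something TMCP aims to change, and that no contact-per-smoker effect or confidence interval is defined in the available text.

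Size and direction are unknown. The odds ratios of 0.78 against 1.32, and 1.50 against 0.60, show only what is possible under assumed rates. In the small-shift case that reverses, both odds ratios are near 1 (0.92 and 1.05).

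Two further inferences should be resisted. One is that the primary outcome was switched after the data were seen: the original prespecification is not in the text, so the documents show an inconsistency and nothing about its cause. The other is that a six-month window suits every site because the summary gives AAC-only at least six months. The dates leave only about 154 days between the last AAC training and the first TMCP training, and site order is in Figure 3, which is not shown. A site late for AAC and early for TMCP would not have six months.

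**What to change.** 1. Reconcile the Project summary and Measures, against the original prespecification, into one stated primary outcome: QL or QL/FFS, denominator, unit (patient or visit), and whether brief advice is co-primary or secondary.
2. Add a supplementary intention-to-treat analysis, labelled post hoc, of contact and enrollment among all current smokers seen in each period. Count no referral or no contact as failure. For QL contact alone, use QL-eligible smokers, whom the EHR identifies from payer data. Use the model in Statistical analyses, with observation windows of equal length in both periods at each site. Set that length from the actual site dates in Figure 3, not at a fixed six months. Note as a limitation that equal windows do not equalise visits per patient, or deal with smokers already referred or recorded as quit in the earlier period.
3. Keep contact among accepted referrals, interpret it as referral yield, and report it beside the acceptance rate.

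The cost is a text correction and one more analysis of EHR data already held, with no new collection. The downsides are lower absolute rates on the wider denominator, loss of some visits outside the windows, and post hoc status.

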#### Statistical analyses

We describe clinician characteristics and patient visits during the study period, and participation in the training and uptake of the TMCP as documented by flowsheet usage. Analyses compared adjusted rates for the AAC+TMCP intervention to AAC only period using a generalized estimating equation (GEE) approach, with robust estimation of variances. Specifically, we modeled the log odds of a particular outcome of interest for a particular patient as a function of intervention status (AAC only vs. TMCP + AAC) at each time point, incorporating random practice site and clinician effects. Three analyses were conducted: 1) intent to treat, 2) per protocol (i.e. clinicians that participated in the TM training), and 3) per documented use of the TMCP approach in a visit. We report rates of performance, odds ratios (OR) and 95% confidence intervals (95% CI). We used 10% as a minimally important difference. Data analyses were performed April 2019 - August 2020. Because this was an educational intervention for clinicians, all of whom ultimately received the training, neither the clinicians nor the study team could be blinded to the group assignment; this design also made it impossible to blind the analyst to group assignment.

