171 the step-wedge implementation. On a rolling basis, data collection indicated the intervention exposure  
172 statuses for each clinic and assessed visit level process outcomes.

[figure not shown]
173 Figure 3 provides more detail about the timing of the AAC and the TMCP intervention  
174 implementation at each of the 8 sites. AAC was the first intervention implemented, and the AAC training  
175 at the first clinic was conducted on February 15, 2017. This training was then conducted at the other  
176 seven clinics at approximately 2-week intervals, but the timing of the training was not randomized.  
177 Trainings were scheduled during regularly scheduled monthly staff meetings for each clinic. The training  
178 date was noted such that a period of pre- and a period of post-training could be defined for each clinic.  
179 Approximately 6 months after the implementation of the AAC in the last site, the TMCP intervention was  
180 implemented, again in a stepped pattern.

181 For the TMCP, the eight clinics were randomized to an implementation time point using the  
182 following approach. A single digit number was assigned to each site. A list of 100 random single digit  
183 numbers was generated and using this list, as a site number came up in the random list it was assigned  
184 the next sequential time point. We encountered two anomalies with randomization of the sites. First,  
185 after implementing the AAC intervention, the site that was randomized to receive the TMCP training  
186 first lost their practice manager. MetroHealth requested that we delay the implementation of the TMCP  
187 in that site due to challenges with daily operations until a new practice manager was effectively in place.  
188 This site was moved to be last. Second, also after the implementation of the AAC intervention, one of  
189 the sites closed. A replacement site was identified to receive the AAC intervention and was included as  
190 the last site for training for the TMCP. The TMCP implementation time points were scheduled as close to  
191 1-month intervals as possible. The first clinic received the TMCP training on October 25, 2017. The  
192 amount of time a clinic was in any one of the three defined study conditions varied but is accounted for  
193 in the analyses.

194 Figure 2. Schema of data collection time points (for EHR, surveys, and in-depth interviews) across all  
195 sites.

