198 Figure 3. AAC and TMCP intervention implementation dates and periods of time before, between and after interventions for each site.

\* Due to technical problems for some clinicians, a second TMCP implementation date was conducted on 11/2

199 \*\* This site was added to replace a site that had been randomized and received the AAC training, but closed shortly after AAC training.

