#### Study sample

The study sample consists of eight sites, 60 clinicians from those sites and all adult patient visits during the study period. Figure 3 shows the timing of the training and implementation of the TMCP interventions at each of the eight study sites. Study data collection began August 2016 and concluded April 2019. One of the original eight clinics that received the AAC training closed shortly afterwards. A replacement site (#8) was identified from a similar neighborhood, and the original clinic was excluded from all analyses. The replacement site received the AAC training and was assigned to receive the TMCP intervention training 1 month after the TMCP training implementation was conducted at the last clinic that had been randomized. This approach allowed sufficient time for data collection and assessment between the implementation of the AAC and the implementation of the TMCP intervention.

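### The analysis model is described both as a GEE with robust variances and as a random-effects model, and with eight randomised sites no cluster level, small-sample correction or reference distribution is stated

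*Combined protocol and SAP*

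**What the plan says.** The model is set out in the Statistical analyses section. Adjusted rates in the two conditions are compared "using a generalized estimating equation (GEE) approach, with robust estimation of variances". The next sentence presents itself as a specification of that model: the log odds of the outcome depend on intervention status "at each time point, incorporating random practice site and clinician effects". Results are reported as odds ratios with 95% confidence intervals. The Project summary speaks only of generalized linear models and adds no detail on variance or clustering.

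Under Participating sites and randomization, the site is the randomised unit. The Study sample section gives the size: "The study sample consists of eight sites, 60 clinicians from those sites and all adult patient visits during the study period".

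The text available names no cluster for the robust variance, working correlation, small-sample correction, reference distribution, degrees of freedom or calendar-time term. On time, Study Design and Timing says that the "amount of time a clinic was in any one of the three defined study conditions varied but is accounted for" in the analyses. That concerns unequal durations in each condition, not a secular trend.

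**The concern.** There are two linked problems.

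1. **The model is not identified.** A GEE estimates a population-averaged odds ratio. A logistic model with random site and clinician effects estimates one conditional on site and clinician. The two differ in value and in how their standard errors behave. A logistic mixed model with empirical standard errors would fit both sentences, but the plan does not say that this is meant.

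2. **Eight clusters are few for a robust variance.** The sandwich estimator is justified for many clusters. With eight it tends to be too small, and the normal critical value of 1.96 is too small as well. Taken at face value, the stated method gives intervals that are too narrow. Clustering on the 60 clinicians instead would give more clusters but would ignore correlation at the level that was randomised.

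At stake is whether a 95% interval that excludes an odds ratio of 1 can be taken at its nominal level.

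**Working it through.** The plan gives no sample size, power, alpha or ICC, so it has no figure to reproduce. The check therefore has two parts: the reference distribution alone, and simulation under no effect.

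**Inputs from the documents.** Eight sites; 60 clinicians; site as randomised unit; TMCP start on 25 October 2017 in steps of about one month; data to April 2019 ("Study data collection began August 2016 and concluded April 2019"); 95% intervals. The Rationale reports that under 42% of referred patients were contacted in prior studies, which is used only to set the base rate.

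**Step 1: reference distribution alone.** If the test statistic follows t with few degrees of freedom but is compared with 1.96:

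- df = 6: P(|t| > 1.96) = 9.8%; critical value 2.447; width ratio 2.447/1.960 = 1.25.
- df = 7: P(|t| > 1.96) = 9.1%; critical value 2.365; width ratio 2.365/1.960 = 1.21.

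**Step 2: null simulations.** The site-clustered sandwich is V = B(Σ sᵢsᵢ′)B, where B is the inverse information and sᵢ the score total of site i. The null is rejected if |b|/SE exceeds the critical value. Everything below that is not listed as a document input is an assumption.

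- *Run A:* base rate 40%; site ICC 0.01 or 0.05; site-by-quarter SD 0 or 0.2 logit; clinician SD 0.3 logit; 5, 15 or 100 patients per site-month; site-size CV 0.5. That makes 2 × 2 × 3 = 12 data scenarios. With independence or exchangeable working correlation and no, linear or quadratic time, there are 12 × 2 × 3 = 72 scenarios of 4,000 replicates each. The site timetable was assumed because Figure 3 is not shown.
- *Run B:* base rate 42%; 2 referred patients per clinician-month (60/8 × 2 = 15 per site-month); 20 months; site ICC 0.01-0.05; clinician ICC 0.01-0.02; cluster autocorrelation 0.8-1.0; independence working correlation; no, linear or categorical time. That is 9 scenarios of 1,500 replicates each.

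Type I error at nominal 5%:

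| Variance and reference | Run A | Run B |
|---|---|---|
| Site sandwich, 1.96 | 11.0-16.2% | 11.0-16.2% |
| Site sandwich, t(6) | not run | 5.0-8.4% |
| Kauermann-Carroll, t(6) | 4.1-6.4% | 3.6-5.6% |
| Mancl-DeRouen, t(6) | 2.2-4.8% | 2.5-3.7% |
| Clinician sandwich, 1.96 | not run | 7.5-22.1% |

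The first row corresponds to coverage of 100 − 16.2 = 83.8% to 100 − 11.0 = 89.0% for a nominal 95% interval.

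**Step 3: cost of correction.** Width ratio = (t × corrected SE)/(1.96 × uncorrected SE). In Run A with t(6) it was 1.35-1.48 for Kauermann-Carroll and 1.47-1.77 for Mancl-DeRouen. Dividing the Kauermann-Carroll range by 1.25 leaves about 1.08-1.18 for the variance correction itself, so most of the widening comes from the t reference.

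**Step 4: the random-effects reading.** A logistic mixed model with random site and clinician and a 1.96 cut-off was run on Run A's data (24 scenarios, 600 replicates each). Type I error was 3.7-5.8% with no site-by-quarter variation. With an SD of 0.2 logit it was 4.5-7.3% at 5 patients per site-month, 8.7-10.2% at 15 and 26.7-33.5% at 100. A mixed model with robust standard errors was not simulated.

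Neither run includes a secular trend. They show nothing about bias from omitting a calendar-time term.

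**The case against.** The strongest reply is that this is an omission and a loosely worded paragraph, not a demonstrated error. No section says that an uncorrected, normal-based test was used. The two sentences may be shorthand for a mixed model, with or without empirical standard errors, and under a mixed model error is near nominal in several scenarios. The document also describes itself as focused on TMCP and points to a fuller report, which was not available here; a part of the protocol between the anticipated problems and the ethics section was not available either. The ICCs, volumes and period variation are all assumed. Using t(6) alone removes much of the excess.

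Most of this stands as a limit on the claim. A reader might infer that the reported intervals are wrong; the documents do not support that, because the variance and reference actually used are unknown. A reader might also infer that the mixed-model reading fails badly. The 26.7-33.5% figure needs both 100 patients per site-month and a site-by-quarter SD of 0.2 logit. No document supports that volume for the primary outcome, which is counted only among patients who accepted a referral. Nor does the plan claim adjustment for calendar trend and then fail to deliver it: it speaks of time in condition, and simply names no trend term.

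What the reply does not remove is that the two sentences describe different models, and that the one named first needs a small-sample method with eight sites. The plan should settle both without recourse to another report.

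**Conclusion.** The point holds as an unresolved model description together with unspecified small-sample inference. Taken at face value, with clustering on site and a normal reference, the stated method has a type I error of about 11-16% instead of 5%, across all the volumes and ICCs tried. Clustering on clinician gave 7.5-22.1% in the one run that tested it. These sizes are indicative, since they rest on assumed base rate, ICCs, volumes and timetable; the absence of a stated cluster level, correction and reference does not. It should be fixed, because the choice decides how far any interval for the TMCP effect can be trusted.

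**What to change.** State one model and say whether its odds ratio is marginal or conditional. The preferred form, closest to the GEE wording, is a marginal logistic GEE with:

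- clustering on site, the randomised unit;
- a named working correlation;
- an explicit calendar-time term, for example linear and quadratic month;
- a small-sample-corrected variance, for example Kauermann-Carroll (Mancl-DeRouen was more conservative in these runs);
- a t reference with stated and justified degrees of freedom, for example sites minus 2 = 6, which is a convention.

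The random-effects wording should then be deleted. If a mixed model was in fact fitted, say so, delete the GEE wording, and state the random effects, the degrees-of-freedom method and whether standard errors are empirical. A site-by-period effect should be considered, but in 12 simulated scenarios adding a site-by-quarter effect still left error at 3.0-9.3%, so it is not a complete remedy.

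No new data are needed and the options are standard. Because the analyses ran to August 2020, corrected intervals should be labelled as a post hoc re-analysis. The cost is intervals about 35-50% wider with Kauermann-Carroll, and up to 77% wider with Mancl-DeRouen, so some results may lose significance.

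Separately, the account of the randomised order needs reconciling. Study Design and Timing says of the site drawn first: "This site was moved to be last". Participating sites and randomization instead has one site placed first at the health system's request and the other seven following the random order. The Figure 3 footnote says of the replacement: "This site was added to replace a site that had been randomized and received the AAC training", and the Study sample section says that it was "assigned to receive the TMCP intervention training 1 month after the TMCP training implementation was conducted at the last clinic that had been randomized". The protocol should say which sites followed the randomised order.
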